3.2 Study Population

This study will include approximately 2700 community-dwelling postmenopausal women aged 50 or above at 8 - 10 participating sites throughout China. A two-stage cluster sampling will be performed for the study. Firstly, geographic regions are divided into 'clusters' and then a randomized stratified sampling will be performed by age group using a computerized random selection on various demographic records (as indicated in Section 3.1) from the participating sites and the communities by which they cover. All subjects are expected to have an interview for questionnaire, vertebral imaging and BMD measurement. To be eligible for the study, participants must fulfill the following inclusion and exclusion criteria (Section 3.3 and 3.4):

3.3 Inclusion Criteria

All inclusion and exclusion criteria will be reviewed by the investigator or qualified designee to ensure that the subject qualifies for the study.

For an inclusion of the study, participant must:

Product: MK-0217A
Protocol/Amendment No.: 911

1. Be age of 50 or above at the time of consent;
2. Live in an urban community in China for over 6 months;
3. Be postmenopausal;

Postmenopause is defined as no menses for at least one year, OR 6 months of spontaneous amenorrhea with serum FSH levels >40 mIU/mL, OR at least 6 months after a surgical bilateral oophorectomy with or without hysterectomy.

4. Be willing to participate by giving informed consent.

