Study Design	Observational, population-based, cross-sectional design with a clustered simple randomization sampling
Study Population	Community-dwelling postmenopausal women aged 50 or over
Study Duration	A 6-9 month of enrollment period
Exposure and Outcome	VF as confirmed by radiology imaging; osteoporosis as suggested by DXA T-score or a proven fragility fracture
Statistical Methods	Prevalence rate by point estimate and 95% CI with model-based statistical analyses for VF risk factors
Sample Size and Power Calculations	A sample size of 2700 women in 5 regions in China. Sample size calculation based on age-specific VF prevalence.
Limitations	Incident VF cannot be assessed in a cross-sectional study; biases for interview-based questionnaire.

1 Background and Rationale

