On the other hand, variations in sample size (CaMOS n=6433, EVOS n=17,342 FRAVO n=842; LAVOS n=1922, DeVOS n=808, Beijing Osteoporosis Project n=402), sampling methodology (age-stratified population-based sampling vs. simple survey sampling), and assessment criteria are seen across the studies. The extent to which these variations represent study bias remains uncertain. Notably, a fine comparison of VF epidemiology between Western societies and China is difficult. Among few population-based studies conducted in China, the Beijing Osteoporosis Project was the first well-documented epidemiology study. The study group performed a randomized sampling and previously validated assessment from the US [36]. However, this study was in a relatively small scale and only represented a local population from the city of Beijing. Another study was the Hong Kong Osteoporosis Study, in which 2178 postmenopausal women have been enrolled [37]. Considering geographic location, lifestyle, and clinical practice, study results may not be generalized to the entire Chinese population. Other cross-sectional studies investigating osteoporosis and fractures neither aimed at a primary collection of VF epidemiology data [39], nor designed adequately to minimize study bias [40]. Therefore, a well-designed, nationwide, population-based epidemiological investigation of the prevalence of vertebral fractures and related risk factors in China is necessary.

2 Objectives and Hypotheses

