2.1 Primary Objective(s) & Hypothesis(es)

To investigate the prevalence of vertebral fractures in community-dwelling postmenopausal women in China

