3 METHODOLOGY

3.1 Summary of Study Design

This study will be designed as an observational, population-based, cross-sectional study. A total of 2700 postmenopausal women over age of 50 inclusive and physically living in a community will be included in the study. As suggested by Chinese local guideline, postmenopausal women are eligible for a subsidized screening program (blood chemistry, radiology and/or DXA assessment) for osteoporosis clinical management. A cluster sampling (two-stage random sampling) by age and geographic region will be performed to represent a geographically generalized Chinese population with specific gender and age groups relevant to postmenopausal osteoporosis and VF prevalence. Subject recruitment will be based on various local demographic records including Government resident lists, local population lists, electoral registers, and health registers by a study invitation and a referral to the investigators at each study center. By 1 onsite visit, an interview, DXA measurement, and thoracic/lumbar spine X-ray will be performed to collect a set of data regarding socioeconomic/medical (interview-based questionnaire), VF assessment (radiographs), and specific densitometric information (BMD DXA) from the participant. No follow-up visit is required for this cross-sectional study unless a spine imaging and/or BMD measurement cannot be made during the visit due to a particular reason in the study or from the subject. The recruitment period is estimated between 6 and 9 months and initiated at any time point during a calendar year, because a seasonal or social impact on the data of interest is minimal. Analyses will be based on epidemiological data and then be expanded to establish a vertebral fracture risk assessment model.

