8.1 Statistical Methods

This section outlines the statistical analysis strategy and procedures for the study. If, after the study has begun, changes are made to primary and/or key secondary hypotheses, or the statistical methods related to those hypotheses, then the protocol will be amended. Changes to exploratory or other non-confirmatory analyses made after the protocol has been finalized, along with an explanation as to when and why they occurred, will be listed in the CSR for the study. Post hoc exploratory analyses will be clearly identified in the CSR. A separate SAP will be created for this study.

8.1.1 Primary Objective(s): Calculation of Epidemiological Measure(s) of Interest (e.g. descriptive statistics, hazard ratios, incidence rates, test/retest reliability)

The study's primary objective is to investigate the prevalence of radiographic vertebral fractures in community-dwelling postmenopausal women in China. Descriptive statistics will be made to statistically address this objective. No hypothesis testing will be applied in the study for this primary objective.

Point estimates (percentage) of prevalence by overall study population and by age group and/or geographic region will be calculated and displayed. A fracture case is defined and counted as the subject with the presence of at least one vertebra classified as grade 1, 2, or 3 semi-quantitatively by Genant's score as agreed by both study radiologists.

Point estimates of prevalence rates by overall and geographic region will be adjusted by a nationwide age distribution using the database from Basic Statistics on National Population Census 2010, National Bureau of Statistics of China [53]. A direct method of adjusting rates will be made to give age-standardized prevalence. Age-standardized rate by regional age distribution data may be calculated subject to site location and will be specified in the SAP before database lock and study analyses.

A corresponding two-sided 95% confidence interval (CI) for each individual point estimate will be given. This 95% CI is based on a direct calculation of the exact binomial distribution. A more conservative method, the Wilson Score CI [52], will be applied to give 95% CIs for all point estimates and compared with the exact binomial distribution.

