8.1.2.1 Prevalence of Osteoporosis

In the study, prevalence of osteoporosis in community-dwelling postmenopausal women in China will be investigated as a secondary objective. Descriptive statistics will be made to statistically address this objective. Point estimates (percentage) and corresponding 95% CI (exact binomial and Wilson score) will be presented for each analysis category and will be adjusted by age distribution in China [53]. Prevalence rates will also be given by age group and geographic region. A case with osteoporosis is counted based on the definition in Section 4.

The prevalence of osteoporosis will be presented as overall and by different diagnostic criteria and will be listed separately to allow an evaluation on the frequency distribution of each individual diagnostic setting in the study population.

The analysis of osteoporosis prevalence is displayed in the Table 8.1.2.1.

Table 8.1.2.1 Statistical Analysis Approaches on the Prevalence of Osteoporosis

Osteoporosis	Rate*	Estimate**	Frequency ***
Overall	Crude/Age-Standardized	Point and 95% CI	Percent
By DXA BMD [^]	Crude/Age-Standardized	Point and 95% CI	Percent
By Fragility Fracture [△]	Crude/Age-Standardized	Point and 95% CI	Percent & Cumulative

* Prevalence rates will be sub-analyzed by age group (50 – 54, 55 – 59, 60 – 65, 65 – 69, 70 – 74, 75 – 79, and 80+; and by < 65 and ≥ 65) and/or geographic region (North, South, Southeast, Southwest, and Central);
 ** Based on exact binomial distribution 95% CI and Wilson Score 95% CI;
 *** Calculation of frequency is relative to overall percent (100%);
 ^ the subject with a T-score ≤ -2.5 as suggested by a DXA measurement
 △ The subject with DXA measurement with a proven non-pathological major fracture as reported by the medical history or as suggested by radiology.

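### Only urban women can enrol, but prevalence is reported for China on nationwide age weights, so the headline claim is wider than the design supports

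*Combined protocol and SAP*

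**What the plan says.** Section 3.3 restricts residence: a participant must "Live in an urban community in China for over 6 months". In the text available, this is the only statement of an urban limit.

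Elsewhere the target is wider:

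- Section 2.1 gives the primary objective as "To investigate the prevalence of vertebral fractures in community-dwelling postmenopausal women in China".
- The Protocol Summary describes the study population as "Community-dwelling postmenopausal women aged 50 or over".
- Section 3.1 says the sampling is meant "to represent a geographically generalized Chinese population with specific gender and age groups".
- Section 1.2 concludes that "a well-designed, nationwide, population-based epidemiological investigation of the prevalence of vertebral fractures and related risk factors in China is necessary".

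For the primary analysis, Section 8.1.1 says that overall and regional point estimates "will be adjusted by a nationwide age distribution using the database from Basic Statistics on National Population Census 2010". For osteoporosis, Section 8.1.2.1 says that estimates "will be adjusted by age distribution in China". One option is left open in Section 8.1.1: "Age-standardized rate by regional age distribution data may be calculated subject to site location", to be specified in the SAP before database lock.

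Section 3.5 stratifies by seven age groups and five regions, with no urban/rural stratum. Section 8.2.3 names the cross-sectional design, low response, dropout and random error, but not the absence of rural women.

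**The concern.** A prevalence survey exists to attach a number to a named population. Here the named population is postmenopausal women in China, and the sampled population is the urban part of it. Direct standardisation changes the age weights only. It cannot supply age-specific rates for women who were never eligible. A reader who sees an overall rate adjusted to the national census, in a study described as nationwide, will take it as China's vertebral fracture prevalence. The interval printed beside it will cover sampling error in urban women and nothing else.

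The weights raise a second question. Only postmenopausal women are enrolled, but the census standard is not restricted to them; the text does not even say that it is limited to women. The youngest band, where some women are not yet postmenopausal and assumed prevalence is lowest, then counts for too much.

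**Working it through.** **The plan's own figures.** The age-group sizes in Table 8.3.1 sum to 44 + 81 + 100 + 90 + 80 + 70 + 53 = 518. Allowing 5% withdrawal, 518 / 0.95 = 545.3, against 545 stated per region. Five regions give 5 × 545 = 2725, against about 2700. Letters: 2700 / (0.60 × 0.95) = 4737, against about 4750. The sample size reproduces and is not in dispute.

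**What the standardised rate estimates.** Let w_i be the national age weights and u_i, r_i the urban and rural prevalences in age band i. The planned rate is Σ w_i u_i. Taking the rural share s as the same at every age, national prevalence is Σ w_i [(1 − s) u_i + s r_i]. The difference is s × (P_urban − P_rural), where both rates use the same age weights. It is zero if the age-specific rates agree. No data in the study bear on r_i.

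**Illustration only.** The documents give neither s nor any rural prevalence, so these inputs are assumptions:

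- Urban prevalence 15%, borrowed from the figure in Section 1.1 for women aged 50 or over.
- Rural share 30% to 60%.
- Rural-to-urban odds ratio 0.67 to 1.5.

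The urban odds are 0.15 / 0.85 = 0.1765. At odds ratio 0.67 the rural odds are 0.1182 and rural prevalence is 10.6%. At 1.5 they are 0.2647 and 20.9%.

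| Rural share | Odds ratio | National prevalence | Urban minus national |
|---|---|---|---|
| 30% | 0.67 | 13.7% | +1.3 points |
| 60% | 0.67 | 12.3% | +2.7 points |
| any | 1.0 | 15.0% | 0 |
| 30% | 1.5 | 16.8% | −1.8 points |
| 60% | 1.5 | 18.6% | −3.6 points |

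For scale, the Clopper-Pearson 95% interval for 15% with n = 2700 is 13.7% to 16.4%, a half-width of about 1.4 points. The table shows that the gap could exceed the sampling error. It does not show that it does.

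**Ages 50-54.** Let w₁ and p₁ be the weight and prevalence of this band, R = Σ w_i p_i, and m the postmenopausal share at 50-54. Restricting the band to postmenopausal women gives

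R_m = [R − (1 − m) w₁ p₁] / [1 − (1 − m) w₁],

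so R_m − R = (1 − m) w₁ (R − p₁) / [1 − (1 − m) w₁]. This is positive whenever p₁ is below R and m is below 1, so the direction is determined. The prevalences are those assumed in Table 8.3.1 (5, 7, 12, 16, 20, 23 and 37%). The census weights are not in the documents, so three sets for women aged 50 and over are assumed, from older to younger:

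- A: 0.20, 0.18, 0.17, 0.15, 0.12, 0.10, 0.08
- B: 0.24, 0.21, 0.17, 0.13, 0.11, 0.08, 0.06
- C: 0.28, 0.23, 0.17, 0.12, 0.09, 0.07, 0.04

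Worked for B: R = 0.1305. With m = 0.6, (0.1305 − 0.4 × 0.24 × 0.05) / (1 − 0.4 × 0.24) = 0.1257 / 0.904 = 0.1390. With m = 0.9, 0.1293 / 0.976 = 0.1325.

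| Weights | R | m = 0.9 | m = 0.6 |
|---|---|---|---|
| A | 14.4% | 14.6% (+0.2) | 15.2% (+0.8) |
| B | 13.1% | 13.2% (+0.2) | 13.9% (+0.9) |
| C | 11.9% | 12.1% (+0.2) | 12.7% (+0.9) |

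**Age bands.** The footnotes to Tables 8.1.1.1 and 8.1.2.1 print 60-65 followed by 65-69. Section 3.5 and Table 8.3.1 use 60-64.

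**The case against.** The strongest reply is that nothing is wrong with the standardisation. National age weights on an urban sample are a legitimate choice. They put the five regions on one scale, and Section 8.1.1 calls the result age-standardised, not national. The scope gap comes from the inclusion criterion and the wording of the objective, and would remain if only crude rates were reported. This is correct, and it limits the point: a reader might infer that the national standard is itself an error, or that the rate estimates nothing useful, and the documents support neither reading. What does not survive the reply is the label. The objective, rationale and design all invite the figure to be read as China's.

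It can also be said that the separate SAP may still define a regional standard, and that crude age-specific and age-by-region rates will be reported, so others can re-weight them. The second part is true and useful. Neither cures the gap: regions are not urban/rural strata, and re-weighting urban rates still gives urban rates.

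On size, one might read the spread from 14.4% to 11.9% across the assumed weight sets as the urban-versus-national error. It is not. None of the three sets is identified as urban or national, so the spread shows only that a standardised rate depends on its weights.

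Finally, the overlap at age 65 might suggest that some women would be counted twice. The strata in Section 3.5, Table 8.3.1 and the split below and from 65 in the same footnotes all settle the matter. It is a clerical slip.

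**Conclusion.** The mismatch is explicit in the text: urban-only eligibility, a target stated as China, a nationwide age standard, and no limitation recorded. If the plan is followed, the headline figure is an urban prevalence on national age weights, presented under a national objective. It is national prevalence only if urban and rural age-specific prevalences are equal, which the study cannot examine. The documents support no size or direction for the difference; the range of +2.7 to −3.6 points rests wholly on assumed rural shares and odds ratios.

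The effect at ages 50-54 is a sound inference with a known direction, downward. It assumes that the census standard is applied unrestricted, as the text reads, and that prevalence at 50-54 is below the overall rate, as Table 8.3.1 assumes. Its size, 0.2 to 0.9 points, depends on the assumed age weights and on postmenopausal shares of 90% to 60%. If the standard also included men, the weights would be wrong in a further way that cannot be sized from the documents.

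**What to change.** 1. State the target as urban community-dwelling postmenopausal women in the objectives, Protocol Summary and conclusions, and add the exclusion of rural women to Section 8.2.3.
2. Report overall and regional rates standardised to the urban female age distribution of the 2010 census, if that table is available; the documents do not show it. Keep the nationwide-standardised rate for comparison, labelled as an urban rate on national age weights. Treat osteoporosis prevalence in the same way.
3. State that the standard population is women, and add a sensitivity analysis that scales the 50-54 weight over a stated range of postmenopausal shares. The share seen at screening should not be relied on: women come to screening after a letter explaining the study, with 40% nonresponse assumed, so self-selection may bias it.
4. Correct 60-65 to 60-64 in the footnotes to Tables 8.1.1.1 and 8.1.2.1.

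This needs changes of wording in the protocol, additional census weights and a few more lines of output. It needs no new data and no change to the sample size. The real cost is a narrower claim.

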3.4 Exclusion Criteria

The participant may not be eligible for the study if one of the followings is met:

1. Race other than Asian;
2. Unwillingness to participate;
3. Cognitive impairment or physical impediment to affect completion of any study procedure;
4. Other potential reasons, in the investigator's discretion, to confound or affect completion of study procedure.

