Fragility Fracture	A fracture that occurred with minimal trauma at a typical site of osteoporotic fracture that would be unlikely to cause fracture in a non-osteoporotic adult.
Postmenopause	No menses for at least one year, OR 6 months of spontaneous amenorrhea with serum FSH levels >40 mIU/mL, OR at least 6 months after a surgical bilateral oophorectomy with or without hysterectomy.
Asthma	A disease characterized by recurrent attacks of breathlessness and wheezing, varying in severity and frequency from person to person, with spirometry showing the FEV1 improves $> 12\%$ following administration of a bronchodilator.
Chronic Obstructive Pulmonary Disease	A lung disease characterized by chronic obstruction of lung airflow that interferes with normal breathing and is not fully reversible, as confirmed in spirometry by a 75-80% of the FVC comes out in the first second and a FEV1/FVC ratio $< 70\%$ with symptoms of the disease.
Diabetes Mellitus	A disease characterized by recurrent or persistent hyperglycemia, and is demonstrating any one of the following: 1. Fasting plasma glucose level ≥ 7.0 mmol/l (126 mg/dl); 2. Plasma glucose ≥ 11.1 mmol/l (200 mg/dl) 2 hours after a 75-g oral glucose load as in a glucose tolerance test; 3. Symptoms of hyperglycemia and casual plasma glucose ≥ 11.1 mmol/l (200 mg/dl); 4. Glycated hemoglobin (HbA1C) ≥ 48 mmol/mol (≥ 6.5 DCCT %).
Confounding	A confounding variable or a confounder is a variable other than the risk factor and outcome under study that is independently related both to the risk factor and to the outcome. A confounder can create an apparent association between the risk factor and outcome or mask a real one

PROTOCOL SUMMARY

Title	An Observational, Cross-Sectional Study Investigating the Prevalence of Vertebral Fractures among Community-Dwelling Postmenopausal Women in China (The Chinese Vertebral Osteoporosis Study, ChiVOS)
Vendor/Collaborator	Not applicable
Rationale	Osteoporosis leads to major fractures including vertebral fractures. Vertebral fractures are a strong predictor of any fracture risk and thus impact the screening of osteoporotic patients and pharmacological treatments. Epidemiological studies investigating the prevalence of vertebral fractures have been increasing in recent years; however, in China, has so far been few.
Primary Objective(s)	To investigate the prevalence of radiographic vertebral fractures in community-dwelling postmenopausal women in China

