8.1.2.2 Risk Factors for Radiographic Vertebral Fracture or Densitometric Osteoporosis

As secondary objectives, all possible factors including socioeconomic status, lifestyle and clinical parameters will be assessed to identify if they are the risk factors of a prevalent vertebral fracture or densitometric osteoporosis in Chinese postmenopausal women.

A two-step statistical modeling will be established to assess the potential risks against the response of analysis interest (dependent variable). Initially, a single logistic regression for bivariate analysis will be used to give a percentage tabulation presenting proportions of case (morphometric vertebral fracture or densitometric osteoporosis) versus control by each analysis parameter. An odds ratio and associated probability (P value) will be given to examine the statistical significance of this independent variable in the model. A P value of 0.25 or less will be the criterion [54] for an entry into a multivariate logistic model for all estimated variables. Also, all clinically relevant variables, regardless of a probability level, will be included in the final model at the discretion of the study team.

Finally, a multivariable logistic regression model will be constructed for both dependent variables. A stepwise backward method to eliminate non-significant variables will be performed until all remaining variables in the model have a P value less than 0.1. The goodness-of-the-fit will be evaluated by using deviance and likelihood ratio tests and Hosmer–Lemeshow test [55] to assess if there is any single important variable missing from the model.

In the bivariate and multivariate analysis, age, BMD, and BMI will be fitted as continuous variables. Geographic region grouping study sites will be fitted as a categorical variable. Due to potential collinearity of BMD to vertebral fracture, BMD will also be introduced as a dichotomous variable (osteoporosis vs. normal and osteopenia). BMI may vary among study sites in the study, odds ratio per unit BMI instead of per standard deviation to minimize the biases upward.

8.1.3 Exploratory Objective(s): Calculation of Epidemiological Measure(s) of Interest (e.g. hazard ratios, incidence rates, test/retest reliability)

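### Exclusion criterion 4 can be read to let investigators exclude women as confounded, so site-specific exclusion of risk-factor carriers could shift prevalence and show up as regional differences

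*Combined protocol and SAP*

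**What the plan says.** Section 3.4 lists four exclusion criteria. The third is "Cognitive impairment or physical impediment to affect completion of any study procedure". The fourth is open-ended: "Other potential reasons, in the investigator's discretion, to confound or affect completion of study procedure". It carries no examples, no limit and no requirement to consult the sponsor.

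Section 3.3 leaves the decision with the site: "All inclusion and exclusion criteria will be reviewed by the investigator or qualified designee". Section 3.2 plans about 2700 women "at 8 - 10 participating sites throughout China", and Table 8.1.1.1 groups the sites into five regions for reporting.

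The List of Definitions describes a confounder as "a variable other than the risk factor and outcome under study that is independently related both to the risk factor and to the outcome". Section 8.1.2.2 says that "all possible factors including socioeconomic status, lifestyle and clinical parameters will be assessed to identify if they are the risk factors". Sections 4 and 6.1.2.1 collect prior fractures, glucocorticoid and antiresorptive treatment, asthma, COPD and diabetes for that purpose.

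**The concern.** The design depends on random selection within region and age group. Criterion 4 acts after selection and after the woman has agreed to take part. If a site takes its reference to confounding in the sense of the protocol's own definition, the natural candidates for exclusion are the exposures that the secondary objectives set out to study. One site could exclude long-term glucocorticoid users while another enrols them, and both would be following the protocol.

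Three outputs are exposed. Overall prevalence would describe a filtered population. Regional prevalence would carry the habits of individual sites, because 8 to 10 sites over five regions is 8/5 = 1.6 to 10/5 = 2 sites per region. The risk-factor models would lose exposed women. The report might show none of this: the bias and limitations sections (8.2.1 and 8.2.3) discuss volunteer effect, nonresponse, recall, measurement and dropout but not discretionary exclusion, and no section asks for exclusion reasons to be recorded or tabulated.

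**Working it through.** **The wording.** *Confound* in criterion 4 could take completion of the procedure as its object. It then adds nothing to *affect*, and criterion 3 already covers cognitive and physical obstacles. Alternatively it refers to associations or results. The List of Definitions uses the term for associations, and section 8.2.3 uses the verb for results and their interpretation. The second reading is therefore open to a site.

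**Inputs from section 8.3.** Table 8.3.1 gives age-group sizes 44, 81, 100, 90, 80, 70 and 53 (sum 518), with assumed prevalences of 5, 7, 12, 16, 20, 23 and 37%. The section also states 5% withdrawal for radiographs, 40% nonresponse and 5% ineligibility.

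**The plan's own figures reproduce.**
- Per region: 518/0.95 = 545.3, against 545 stated.
- Total: 5 × 545 = 2725, against about 2700.
- Letters: 2700/(0.60 × 0.95) = 4737, against about 4750.

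The 5% covers all ineligibility. The documents give no rate for criterion 4, so the exclusion rates and risks below are assumptions.

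**Baseline.** The weighted prevalence in Table 8.3.1 is P = 85.98/518 = 16.6%.

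**Scenario A: a fraction e = 5% is excluded, with fracture prevalence q.** Observed prevalence = (P − e·q)/(1 − e). The spurious odds ratio (OR) compares an unaffected region with one that excludes in this way.

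| q relative to P | Observed | Shift (points) | Spurious OR |
|---|---|---|---|
| 1.5 times (24.9%) | 16.2% | 0.4 | 1.03 |
| 2 times (33.2%) | 15.7% | 0.9 | 1.07 |
| 3 times (49.8%) | 14.9% | 1.7 | 1.14 |
| every excluded woman has a fracture | 12.2% | 4.4 | 1.43 |

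The last row is the bound for 5% exclusion, not a realistic case.

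**Scenario B: 10% of women carry a factor with a given OR for fracture.** Prevalence r among non-carriers solves 0.9·r + 0.1·OR·r/(1 + (OR − 1)·r) = P.
- OR 2: r = 15.5% and carriers 26.8%. Dropping all carriers gives 15.5% (shift 1.1). Dropping half gives (0.9 × 0.1547 + 0.05 × 0.2679)/0.95 = 16.1% (shift 0.5).
- OR 3: r = 14.7%. Dropping all carriers gives a shift of 1.9.

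A and B together give the range of 0.4 to 1.9 points. Crossing the harshest settings, 10% excluded at three times average risk, would give 12.9% (shift 3.7). That is twice the plan's total ineligibility rate applied to a very high-risk group.

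**Share reaching the national estimate.** With equal-sized sites, one site dropping every carrier moves the national figure by its own shift divided by the number of sites:
- OR 2: 1.13/10 = 0.11 to 1.13/8 = 0.14 points.
- OR 3: 1.94/10 = 0.19 to 1.94/8 = 0.24 points.

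**Yardsticks.** Nominal 95% half-widths, 1.96·√(P(1 − P)/n), ignoring any design effect:
- National, n = 2700 × 0.95 = 2565: 1.4 points.
- Region, n = 518: 3.2 points.
- Single site, n = 2565/8 to 2565/10: 4.1 to 4.6 points.

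**The case against.** The best defence is that both verbs in criterion 4 govern completion of the procedure, in parallel with criterion 3, and that it is only a residual clause. The protocol's intent also points towards inclusion: it sets out to assess all possible factors, and section 6.1.2.2 requires DXA even in women with known spine deformities unless waived after consultation with the sponsor. A site that excluded glucocorticoid users would be working against a stated objective. This makes wide use of the broad reading less likely. It does not close that reading, and the DXA rule does not restrict criterion 4.

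Several stronger inferences are tempting but not supported:

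- **That every exclusion is optional**, because section 3.4 opens with "The participant may not be eligible for the study if one of the followings is met". Sections 3.2, 3.3 and 6.1.4.1 require participants to meet the criteria, so this is loose phrasing.
- **That investigators decide knowing the fracture history.** Section 6.1.1.3 describes a brief review that names menstrual history, physical ability and cognitive status, not fractures. Such knowledge is possible, since medical records are consulted and the section 5 flow chart also marks the questionnaire at screening, but it is not established.
- **That prevalence is necessarily biased downward.** Excluding high-risk women lowers it; excluding treated women could move it either way.
- **That a shift of up to 1.9 points exceeds the national half-width of 1.4.** This sets a shift at the sites that exclude against national precision. The comparison is fair only if all sites exclude in the same way, which is not the between-site variation at issue.
- **That the risk-factor odds ratios are thereby biased.** Exclusion on an exposure that is itself in the model mainly costs precision.

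**Conclusion.** The point stands as a defect in what the wording permits, not as a demonstrated bias. Criterion 4 allows a discretionary filter on the random sample for a reason that has no place in a prevalence survey, and nothing in the plan would reveal its use.

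The likely size is modest: about 0.4 to 1.9 points wherever the practice is applied, about 0.1 to 0.2 points nationally if one site does it, and a spurious regional OR of about 1.03 to 1.14 if 5% exclusion is confined to one region. These figures rest on assumed exclusion rates and risks. Within the 5% scenario, a spurious OR in the 1.40 to 1.50 range for which section 8.3 claims power arises only if every excluded woman has a fracture. Unlike sampling error, the shift does not shrink as more women are enrolled. The change is worth making because it protects the primary estimate at almost no cost.

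**What to change.** Amend section 3.4 and the analysis plan in three ways:

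1. Delete *confound or* from criterion 4, so that it covers only other reasons that prevent completion of the study procedures: questionnaire, DXA and spine radiographs. All three should be named, because the secondary objectives depend on the first two.
2. State that, apart from criterion 3, a comorbidity, medication or fracture history is not in itself a ground for exclusion and is handled in the section 8.1.2.2 models. The carve-out is needed because criterion 3 excludes for cognitive impairment.
3. Record the reason for each exclusion under criterion 4 and tabulate these by site, region and age group. The separate SAP announced in section 8.1 is a natural place to specify the table.

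The cost is a few words in an amendment, one field on the screening record and one table. Participants undergo no additional procedures, and the variables concerned are already collected and modelled.
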